- Time taken by the procedure measured in seconds.

ELIGIBILITY CRITERIA

All patients with existing plasma cell disorders and no history of psychiatric disorders and can receive conscious sedation are eligible to participate in the trial.

EXCLUSION CRITERIA

Pregnant women are excluded from participating in this study due to the uncertainty in the positioning of pregnant patients for the procedure.

METHODOLOGY

PATIENT IDENTIFICATION:

The patients with plasma cell disorders undergoing bone marrow biopsy procedure at the procedure bay in Winship Cancer Institute will be identified weekly. The list of prospective patients will be shared among the clinical and research team.

SEDATION/ANALGESIA:

The eligible patients would be assessed whether they can receive conscious sedation. Any contraindication to receive conscious sedation will exclude the patients from the study. Standard agents for conscious sedation as approved by the Emory University will be used. Standard personnel who can administer the conscious sedation will be able to perform the sedation and bone marrow biopsy.

APPROACH:

The eligible patients on the day of the procedure will be approached and the study strategy and the procedures are explained to the patients. Informed consent is given to the patients and adequate time is given for the patient and family members to review and make a decision regarding participating in the study. Voluntary patients interested in participating in this non-therapeutic study after signing consents will be randomized to the power drill arm or the traditional (Jamshidi) bone marrow biopsy arm.

RANDOMIZATION:

All the study participants are randomized by using a shuffling card method. 100 cards with predestinated procedure name (50 with traditional and 50 with powered biopsy) printed on them are shuffled and patient is asked to pick one card from the deck and he/she will be placed in the respective group. Every time the card is picked it is not replaced into the deck. This helps us to approximately achieve a balance in number of patients in each of the study groups.

QUESTIONNAIRES:

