Patients are asked to fill out the VAS pain questionnaire before the start of the procedure and 30 minutes after the procedure, day 1, day 3, and day 7. Subject will be given a VAS pain scale to score the intensity of the pain. Majority of the patients will return to Winship Cancer Institute in a few weeks to discuss the results of the bone marrow biopsy. Questionnaires will be collected during this visit. In the event that the patient is not returning to Winship, patients will use the return stamped envelope provided on the day of the procedure to return the questionnaires. Patients will be contacted over the phone as a reminder to return the completed the VAS questionnaire if not received during the follow-up clinic visit. For the secondary endpoint of time taken for the procedure, we will use a stopwatch from the beginning to the completion of the procedure (skin to skin)

Variables to be considered during analysis: Sample size, length of procedure, pain intensity before procedure and at different time points after procedure, age, gender and BMI.

Statistical methods: Analyzed using a SAS 9.1 version. Continuous variables like, the bone marrow biopsy length, and time taken for procedure are studied with mean, median, range and standard deviation and compared by two-sample t-test. While the categorical variables, pain is studied with χ^2 or Mann Whitney U test or Fisher's exact test.

DATA SAFETY MONITORING PLAN

The bone marrow drill procedure is done as a SOC at our institution, and we have established the safety of the procedure without any untoward events over the last 3-4 years. We have not proposed an interim analysis for futility or efficacy, taking into consideration that the final results of the study if fully

conducted will not harm a patient. [name] will be the primary responsibility for overseeing the data and the interim analysis.

DATA STORAGE AND PROTECTION

All data will be maintained on the REDCap database supported by the Research and Woodruff Health Sciences IT (RWIT) Division at Emory University.. Access to the server is protected by (firewalls, encryption etc) and all accounts will be password protected.

Confidentiality

Your name, telephone number, social security number, residential and mailing addresses will be collected from your medical record for study related contact. Laboratory results, billing, clinical, radiology, physician, and hospital records will also be collected from your medical record.

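### Secondary pain endpoint: pre-procedure VAS is collected but has no role in the analysis; adjusting for it would be a cheap gain in precision if the form is completed before the allocation card is drawn

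*Combined protocol and SAP*

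**What the plan says.** Pain is secondary endpoint (a) under Aims, and Outcomes describes it as a 10-point VAS. The Questionnaires section asks patients to complete the "VAS pain questionnaire before the start of the procedure and 30 minutes after the procedure, day 1, day 3, and day 7". The paragraph on variables for the analysis lists "pain intensity before procedure and at different time points after procedure, age, gender and BMI" and assigns none of them a role. The Statistical methods paragraph then says: "While the categorical variables, pain is studied with χ^2 or Mann Whitney U test or Fisher's exact test". It mentions no covariate, model, stratified test or change score.

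Two other sections bear on the baseline score. Under Approach, "The eligible patients on the day of the procedure will be approached", so consent, randomization and biopsy can all fall on one day. Under Randomization, cards with the procedure name "printed on them are shuffled and patient is asked to pick one card from the deck". The baseline form is placed only before the procedure starts, not before or after the draw.

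**The concern.** A baseline measured on the same scale as the outcome is usually the most useful covariate a pain comparison can have. Here it is collected at the sponsor's expense and then left out of every named test.

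Two things follow. First, precision may be given up on an endpoint with at most 50 patients per arm. Second, because the role is undefined, the analyst could later choose raw scores or change from baseline. Those choices can differ widely in power, and which is better depends on a correlation nobody has stated. The choice should be made before the data are seen.

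The order of the form and the draw also matters. A score given by a patient who already knows the device may reflect that knowledge, and such a score is not a safe covariate.

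**Working it through.** **Inputs.** From the documents: 50 cards per arm (Randomization); one pre-procedure and four post-procedure VAS scores (Questionnaires); a 10-point scale (Outcomes). Not in the documents, so assumed: two-sided 5% level; VAS distribution; treatment effect; correlation ρ between pre- and post-procedure scores, shown from 0 to 0.7. The plan gives no sample-size or power figure for pain, so there is nothing to reproduce.

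**Step 1: normal approximation.** Relative to the raw post-procedure score, the variance of the comparison is multiplied by 1 − ρ² with ANCOVA and by 2(1 − ρ) with a change score. With an assumed standardised difference of 0.5 and 50 per arm, power is Φ(0.5 × √(50/2) / √v − 1.96) = Φ(2.5/√v − 1.96), where v is that multiplier. The raw score (v = 1) gives Φ(0.54) = 70.5% at every ρ.

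| ρ | ANCOVA v | ANCOVA power | Change v | Change power |
|---|---|---|---|---|
| 0 | 1.00 | 70.5% | 2.0 | 42.4% |
| 0.3 | 0.91 | 74.6% | 1.4 | 56.1% |
| 0.5 | 0.75 | 82.3% | 1.0 | 70.5% |
| 0.7 | 0.51 | 93.8% | 0.6 | 89.8% |

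The change score only breaks even with the raw score at ρ = 0.5.

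**Step 2: simulation on bounded scores.** Real VAS scores are bounded and may be skewed, so scores were simulated from a latent distribution, then rounded and clipped to 0–10 (10,000 replicates per cell, Monte Carlo standard error at most 0.5 points). The near-normal shapes have latent SD 2.5, reference-arm mean 3 and shift 1.25. The skewed shapes are log-normal with log SD 1; the log shift is 0.6 in the first two and 0.55 in the third. Rank ANCOVA ranks the post- and pre-procedure scores, regresses one on the other and compares the residuals between arms. Power (%) at latent ρ = 0 / 0.3 / 0.5 / 0.7:

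| Shape (share of baselines at zero) | Raw Mann-Whitney | Mann-Whitney on change | Linear ANCOVA | Rank ANCOVA |
|---|---|---|---|---|
| Near-normal (16%) | 67/67/67/67 | 41/53/67/85 | 68/72/79/91 | 67/70/77/89 |
| Near-normal (84%) | 67/66/68/66 | 63/68/73/75 | 68/69/74/78 | 67/68/72/76 |
| Skewed (84%) | 80/81/79/81 | 76/81/84/87 | 73/76/78/86 | 80/82/84/88 |
| Skewed (42%) | 80/80/80/81 | 63/74/85/94 | 74/75/81/90 | 80/82/88/94 |
| Skewed (24%) | 74/74/74/74 | 54/65/77/90 | 68/71/77/87 | 74/77/83/92 |

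Before rounding, rank ANCOVA minus raw Mann-Whitney is −0.5 to 0.0 points at ρ = 0, 1.2 to 3.4 at 0.3, 4.2 to 10.5 at 0.5 and 7.2 to 22.5 at 0.7. Smaller simulations of some of these shapes gave similar values (for example +3.9 at 0.5 with a mostly zero baseline). A cautious summary is about 0, 1 to 4, 3 to 11 and 7 to 23 points. If only 40 per arm return forms (assumed), the differences are −0.4 to 0.1, 0.6 to 3.3, 4.3 to 10.5 and 8.8 to 24.5.

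Change-score Mann-Whitney is 4 to 26 points below raw at ρ = 0 and 6 to 19 above it at 0.7. These figures depend on shape and direction of effect: with the effect set as a reduction, two shapes gave losses of 30 and 8 points at ρ = 0. Linear ANCOVA loses 6 to 7 points on the skewed shapes at ρ = 0, so it is not a safe main method either.

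**Step 3: type I error.** When baseline is independent of arm, rank ANCOVA rejects in 4.6 to 5.5% of null trials at 50 per arm and raw Mann-Whitney in 4.4 to 5.4%. If knowledge of the device shifts the baseline score in one arm and post-procedure pain does not differ, the picture changes. With an assumed shift of 0.5 VAS points, rank ANCOVA rejects in about 5 to 14% as latent ρ goes from 0.3 to 0.7; with 1 point, in about 7 to 39%. Raw Mann-Whitney stays near 5%.

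**The case against.** The strongest objection is that adjustment could make things worse. The present tests are valid whatever the order of form and draw. An adjusted test is valid only if baseline precedes knowledge of the device, and Step 3 shows how large the error could become otherwise. This stands, and it makes the order a precondition for adjusting.

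A reader might infer from this that baseline scores will in fact be influenced by allocation. The documents do not say so. They leave the order open, and the sizes of shift in Step 3 are assumed.

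A second objection is that the gain may be nil. Every figure rests on assumed inputs, and nothing shows that background pain predicts pain after the biopsy. With 84% of baselines at zero, a latent correlation of 0.5 is an observed rank correlation of only about 0.31, and 0.7 about 0.44. This also stands. It argues for a method that costs almost nothing when the baseline is uninformative, as rank ANCOVA does at ρ = 0. Skew is plausible, since "Any contraindication to receive conscious sedation will exclude the patients from the study", but that is inference, not a stated distribution.

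Third, the plan already lists pre-procedure pain for consideration. That may signal an intention to use it, but it is not a method.

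Fourth, rank ANCOVA alone gives a p-value without an effect size, and four post-procedure times leave open which one counts. Both are fair and are met in the fix.

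**Conclusion.** The point holds as an improvement to one secondary endpoint. The plan collects a baseline and gives it no role, and a better use of it is available with no added patients, visits or data fields. The likely gain in power at 50 per arm runs from nothing to about 23 points, depending on a correlation and score distribution that the documents do not give, and sits at the low end if most patients report no pain beforehand. An unadjusted change score is not a safe default.

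A reader might go further and infer that the planned pain tests are biased or invalid. They are not: randomization protects the unadjusted comparison, and the loss is precision. Nor does the point reach core length, artifacts or procedure time. Nor does it show that the trial is underpowered for pain, since no target effect or power is stated.

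**What to change.** 1. In Randomization and Questionnaires, state that the pre-procedure VAS form is completed before the card is drawn. Adjustment depends on this.
2. In Statistical methods, state that post-procedure VAS is compared between arms by rank ANCOVA on pre-procedure VAS, at one main post-procedure time point that the sponsor names in advance, with the other times secondary. Report raw Mann-Whitney at the same time as a sensitivity analysis, and make it the main test if the baseline form was not completed before the draw.
3. Report an adjusted effect estimate with a 95% confidence interval beside the p-value, for example an odds ratio from a proportional-odds model with device and pre-procedure VAS, or an adjusted mean VAS difference. In limited runs the proportional-odds likelihood-ratio test had type I error of 4.0 to 7.2% (standard error about 0.9), which is why rank ANCOVA is preferred for the test itself.

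The cost is SAP wording and a small change to same-day workflow, with possibly little return if baseline scores are mostly zero.

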Title: Comparison of quality of bone marrow biopsy and patient convenience and pain control by a battery powered drill versus conventional methods in patients with plasma cell disorders

PRINCIPAL INVESTIGATOR:

Name:	[name]		
Institution:	Winship Cancer Institute		
Address:	[name]		
	City: Atlanta	State: Georgia	Zip: 30322
Email:	[contact]	[contact]	[contact]

AIMS

1. Primary endpoint - Assessing the quality and quantity of bone marrow core biopsies.
2. Secondary endpoint –
 - (a) Assessing the nature of pain by established VAS questionnaires.
 - (b) Timing of the actual procedure

BACKGROUND:

Since the introduction of Jamshidi needle in 1971, we have not seen any advances in bone marrow sampling technology (Jamshidi & Swaim, 1971). In 2007, a new battery-powered bone marrow biopsy system was developed by OnControl Vidacare Corporation, Shavano Park, Texas, USA. This technology using a battery-powered drill to operate the needle to gain access to the posterior iliac bone was approved by the United States Food and Drug Administration (FDA) and currently commercially available.

The traditional method for gaining bone marrow involves grinding a needle by hand through a patient's skin and bone.

The oncontrol bone marrow biopsy device consists of a powered driver and biopsy needle set. The lithium battery-powered driver resembles a small hand-held drill and drives a needle into medullary cavity of the top ridge of your rear hip bone (iliac crest) to obtain the soft tissue located in the marrow space . The

needle set consists of two parts: an outer cannula, 11 gauge × 4 inches (102 mm) long; and a bevel-tip inner stylet, used to penetrate the cortex of the bone.

This method is most commonly carried out on the top ridge of the rear hip bone with a patient in the right or left lateral position. Procedure performed under anesthesia (medication that causes numbness), local anesthesia is provided via infiltrating an adequate area of the periosteum. Commonly a skin insertion is made (with a lancet) and the needle is inserted through the skin, once the needle touches the bone the drill is started. During the procedure, you will hear a sound and feel the vibration of the needle. After the powered drill advances the needle into the marrow cavity the inner stylet is removed and the threaded cannula grabs the marrow.

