Marrow has both solid and liquid parts. Aspiration is the procedure used to collect the liquid part of the marrow. If the solid portion of the bone is sampled, this is called a biopsy.

In the aspiration, an incision will be made and a needle inserted through the skin. Once the needle touches the bone, the power driver will be started and you may feel some vibration. Within a few seconds, your doctor will stop and take a sample of liquid marrow with a syringe.

For the biopsy, after the aspirate has been collected, the power driver is restarted and, in a matter of seconds, your doctor will capture a sample of the solid marrow

Few randomized controlled trials (RCTs) compared the use of the battery powered bone marrow biopsy system to the traditional manual methods however they have certain limitations. Though the use of a powered drill is justified in selected patients, the results are not uniform. Swords et al reported that powered drill significantly reduces needle insertion pain and procedural time when compared to a manual technique (Swords et al., 2011) delivering similar quality of specimens by both method (Swords et al., 2010). In another RCT by Read et al evaluating hematologists-in-training, they were significantly faster and sampling was superior in quality when performed with the power drill (Reed et al., 2011). In the most recent RCT by Bucher et al, both methods produce similar results. In the absence of using conscious sedation, reported pain during the procedure is lower with the powered drill (Bucher et al., 2013). The limitations with these RCTs included relatively small number of patients, significant heterogeneity in patient population, and inclusion of patients with all indications. At our institution we have adapted to the power drill system and majority of the patients receive conscious sedation (by personal communication). We are proposing to conduct a RCT to identify the optimal procedure in patients with plasma cell disorders undergoing bone marrow biopsy due to technical challenges with concomitant osteoporosis/ osteopenia and ongoing bone loss in this particular set of patients.

PATIENTS AND METHODS:

Design

Prospective randomized control trial in multiple myeloma patients.

Outcomes:

- Bone marrow core biopsy length (in mm) and artifacts assessed by the pathologist blinded for the sample.
- Intensity of Pain as measured via VAS (visual analogue scale) for pain, a 10 point scale.

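### Pain on the 10-point VAS is classed as categorical, with three alternative tests and four post-procedure ratings; no test, cut-point, lead rating or multiplicity rule is fixed, and two of the three tests waste information.

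*Combined protocol and SAP*

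**What the plan says.** - AIMS lists pain as secondary endpoint (a): "Assessing the nature of pain by established VAS questionnaires". The study title also names pain control as one of the comparisons.
- Outcomes (under PATIENTS AND METHODS) defines the measure: "Intensity of Pain as measured via VAS (visual analogue scale) for pain, a 10 point scale". The end points and step of the scale are not given.
- QUESTIONNAIRES sets the rating times: "before the start of the procedure and 30 minutes after the procedure, day 1, day 3, and day 7". That is one rating before the procedure and four after it.
- The list of analysis variables includes "pain intensity before procedure and at different time points after procedure, age, gender and BMI". It names no lead time, change score, summary measure or model.
- Statistical methods assigns core length and procedure time to one test ("compared by two-sample t-test"). It then continues "While the categorical variables, pain is studied with" and gives chi-square, followed by "Mann Whitney U test or Fisher's exact test". No rule chooses among the three.
- RANDOMIZATION gives the only size figure, a deck of 100 cards: "50 with traditional and 50 with powered biopsy".

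No VAS category or cut-point, significance level or multiplicity rule for pain appears anywhere.

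**The concern.** An intensity score carries order: 7 is worse than 4, and 4 is worse than 2. Calling it categorical opens the way to two tests that do not use that order well. Chi-square on the table of scores treats each score as an unrelated label. Fisher's exact test in its 2x2 form needs a threshold, and someone would have to choose it.

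The second problem is the number of routes to a result. Three tests, an unstated set of cuts and four ratings are all permitted, and nothing ranks them. Patients draw a card printed with the procedure, and the only blinding described is the pathologist's, which does not cover pain. Nothing in the plan therefore keeps the choice of test, cut and rating away from people who know the allocation.

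At stake is the pain comparison. The Background says that earlier trials of the drill gave results that were not uniform. A pain finding picked from many possible analyses would not help to settle the question, and a real difference could be missed if a weak test were used.

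**Working it through.** **No figure to reproduce.** The plan states no alpha, power, effect size, SD or cut for pain. Only the 50 + 50 allocation comes from the documents (RANDOMIZATION).

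**Assumed inputs.** Two-sided 5%; scores are normal values with SD 2.5, rounded to integers and clipped to 0-10; mean 3 or 4 in one arm for power, and 3 to 4 in both arms for false positives; correlation between ratings 0.3 to 0.9. Each scenario used 2,000 to 4,000 simulated trials.

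**Step 1. Power at one rating, 1.25-point shift.** The standardised difference is 1.25 / 2.5 = 0.5. The normal approximation gives Φ(0.5 × √(50/2) − 1.96) = Φ(2.50 − 1.96) = Φ(0.54) ≈ 0.71. On rounded, clipped scores the simulation gives:

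| Test | Power, 1.25 points | Power, 1.5 points |
|---|---|---|
| t-test (reference) | 0.67-0.68 | 0.83 |
| Mann-Whitney U | 0.66-0.68 | 0.82 |
| Fisher, cut at 4 or more | 0.40-0.47 | 0.60 |
| Fisher, cut at 7 or more | 0.07-0.20 | 0.26 |
| Chi-square on the full score table | 0.25-0.26 | 0.40 |

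Mann-Whitney gives up almost nothing against the t-test. The other two listed tests give up a great deal, and the Fisher result depends heavily on the cut.

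**Step 2. False positives with no true difference.** For four independent ratings at 5% each, the chance of at least one is 1 − 0.95⁴ = 0.185. Ratings on the same patient are correlated, so the simulated values are mostly lower:

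| What is left open | Chance of at least one p < 0.05 |
|---|---|
| Nothing: Mann-Whitney, one rating fixed in advance | about 0.05 |
| Three tests, one rating, cut fixed at 4 or more | about 0.09 |
| Mann-Whitney, any of four ratings | 0.10-0.19 |
| Three tests, four ratings, cut fixed at 4 or more | 0.22-0.31 |
| Three tests, four ratings, cut chosen from 3 to 7 | 0.30-0.43 |
| As above, wider choice of cuts | up to about 0.48 |

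Within each multi-rating row, the lower end belongs to correlation 0.9 and the upper end to 0.3 (or to independence for Mann-Whitney at any of four).

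**Step 3. Falling pain.** The rows above assume the same mean pain at all four ratings. If latent means fall over the week (assumed 3, 2, 1, 0 or 3, 2, 0, −1, correlation 0.6-0.8), a full search gives about 0.29-0.35. The inflation shrinks but remains.

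**The case against.** The strongest reply is that a suitable test is already in the plan. Mann-Whitney U uses the order of the scores, needs no cut, and holds about 5% at a single rating. A reader might infer that every listed test is unsuitable, or that the pain result must be either weak or selected after the fact. The documents do not support that: an analyst who used Mann-Whitney at a rating fixed in advance would have a sound result. This part of the objection stands. The fault is that nothing commits the analyst to that route.

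Second, the sentence is badly formed. It can be read as covering categorical variables and pain together, with chi-square and Fisher meant for items such as gender and Mann-Whitney for pain. The literal wording classes pain as categorical, but the other reading is possible. Even so, the plan would still not say which test belongs to pain, and the open choice of rating would remain.

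Third, the largest false-positive figures describe a deliberate search through every test, cut and rating, on inputs the documents do not supply. That is fair, and they should be read as an upper range rather than a forecast. The 10-19% for Mann-Whitney alone needs only a free choice among four ratings.

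Finally, it is tempting to say that the 30-minute rating must lead because it alone is made in the clinic. QUESTIONNAIRES does not say where any rating is completed, so that is an inference. Patients must also be able to receive conscious sedation, which could affect an early rating. The documents do not settle which rating is best.

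**Conclusion.** The point holds for a secondary endpoint and should be corrected. The plan labels an ordered score as categorical, lists two tests that use it poorly beside one that uses it well, and fixes neither the test nor the cut nor the rating.

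Under the assumed inputs, using chi-square in place of Mann-Whitney would cut power for a 1.25-point shift from about two in three to about one in four. Leaving only the rating open would raise the false-positive rate from 5% to about 10-19%, and leaving everything open would raise it to about 30-48%. The exact sizes depend on the assumed SD, means and correlations. The ordering of the three tests was the same in every power scenario tried, and the inflation appeared at every correlation tried.

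A reader might infer that the trial's main result is compromised. It is not: the core-biopsy comparison does not depend on the pain analysis.

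**What to change.** In Statistical methods:

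1. Take pain out of the categorical variables and state that the VAS is analysed as an ordered score, giving its minimum, maximum and step.
2. Delete chi-square and Fisher's exact test for pain, and make Mann-Whitney U the pain test.
3. Name in advance either one post-procedure rating (for example 30 minutes) or one defined summary over the four ratings as the pain endpoint that supports the conclusion. Report the other ratings descriptively.

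**Cost.** A few sentences, with no new data or patients and almost no loss of power (Mann-Whitney 0.66-0.68 against 0.67-0.68 for a t-test). A difference seen only at a non-lead rating becomes supportive evidence. If 30 minutes is chosen, the rating may be affected by sedation; if a summary is chosen, its formula and the handling of missing ratings must be written down. The sponsor should make that choice before any comparison of pain by arm is seen.

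### Does the stray mention of an interim analysis in the monitoring plan put the type I error at risk?

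*Combined protocol and SAP*

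**What the plan says.** Two consecutive sentences in the Data Safety Monitoring Plan bear on this point. The first reads "We have not proposed an interim analysis for futility or efficacy", and gives as its reason "taking into consideration that the final results of the study if fully" conducted, will not harm a patient. The same section notes that the drill procedure is already standard of care at the institution. The second sentence says that a named individual "will be the primary responsibility for overseeing the data and the interim analysis".

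No other section mentions an interim analysis. The statistical methods paragraph in the Methodology section describes only comparisons of the collected data. Core length and procedure time are "compared by two-sample t-test", and pain is analysed by categorical or rank methods. No significance level is given. The Randomization section fixes the intended size through the deck: "100 cards with predestinated procedure name (50 with traditional and 50 with powered biopsy) printed on them are shuffled".

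**The concern.** The second sentence uses the definite article, as though a particular interim analysis existed, directly after the plan has said that none is proposed for futility or efficacy. Someone could take it as permission to compare the arms partway through. With no boundary or alpha allocation in the plan, both that comparison and the final one would be made at the full significance level.

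Little in the trial's conduct would prevent it. Allocation is known to the patient ("patient is asked to pick one card from the deck and he/she will be placed in the respective group"), and no masking is described for the operator or for whoever oversees the data. At stake would be the false-positive rate of the primary comparison if an early look could lead to stopping or to announcing a result.

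**Working it through.** **Step 1. Compare the two sentences.**

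- The first rules out interim analysis for two stated purposes, futility and efficacy. It is silent on safety.
- The second names no purpose, endpoint, time or decision. It sits under a data safety heading and couples the interim analysis with overseeing the data.
- The two are compatible if the second refers to a safety or data-quality review. If it refers to an efficacy look, it conflicts with the only explicit rule on the subject.
- The reason given in the first sentence takes the study as fully conducted, which fits a single final analysis.

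**Step 2. Look for anything that would make an efficacy look operational.** The protocol gives no look time, endpoint, boundary, alpha allocation, stopping rule, committee or provision for an early claim.

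**Step 3. Size the consequence if a look were taken anyway.** There is no figure in the plan to reproduce. The inputs are:

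- 50 patients per arm, from the card deck.
- Two-sample t-test, from the statistical methods.
- Two-sided 5% at each look. This is an assumption, because no alpha is stated.
- Look time t, as a fraction of the final information. This is also an assumption, shown as a range.

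For an interim statistic Z1 and a final statistic Z2 with no true difference, the correlation is √(t/1) and the overall error is 1 − P(|Z1| < 1.96 and |Z2| < 1.96).

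| Unadjusted looks | Correlation of Z1 and Z2 | Overall type I error |
|---|---|---|
| Final only (the plan as written) | – | 5.0% |
| One interim at t = 0.25 | √0.25 = 0.50 | 9.1% |
| One interim at t = 0.50 | √0.50 = 0.71 | 8.3% |
| One interim at t = 0.75 | √0.75 = 0.87 | 7.3% |
| Two equally spaced interims | – | 10.7% |
| Three equally spaced interims | – | 12.6% |

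The one-interim rows come from the bivariate normal distribution, and the last two rows from simulation. As a check, 200,000 simulated trials with t-tests at 25 and then 50 per arm gave 8.3% for the two tests together and 5.0% for the final test alone.

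**Step 4. Match the rows to the plan.** Every row above 5.0% requires a by-arm efficacy comparison that could end the trial or produce a claim. Steps 1 and 2 show that the plan provides for none, so the first row applies. A safety review that does not test the endpoints for stopping or claiming also leaves the first row in place.

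**The case for a change.** The best argument for a change is that the sentence is imperfect on every reading. If it means a safety review, none is described. If it is template residue, it assigns responsibility for something that does not exist. If it means an efficacy look, it conflicts with the sentence before it. The rationale given for having no interim analysis concerns patient harm and does not mention error control. By-arm data are probably within the overseer's reach. Core length and artifacts are read blind ("artifacts assessed by the pathologist blinded for the sample"), which protects the measurement but would not stop someone from comparing the arms afterwards. Correcting the sentence would cost almost nothing.

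Most of this stands as a comment on drafting. The term is undefined, the arithmetic is right for its scenario, and removing the phrase would be harmless tidying. What does not stand is the step from an unexplained noun phrase to an authorised efficacy look. The inflation needs three things: a comparison of arms on an endpoint, a decision attached to it, and no adjustment. The plan supplies no decision, and it expressly says that an efficacy or futility comparison is not proposed.

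A replacement calling for safety review pooled across arms would go beyond the documents. They describe no such review, and pooling could hide a difference between two devices.

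**Conclusion.** No change to the plan follows. This is a clerical inconsistency: one undefined phrase next to an explicit statement that excludes efficacy and futility looks. A team following the protocol makes a single final comparison, and its type I error is the nominal level, 5% under the assumed two-sided alpha. Deleting or explaining the phrase would alter no estimate, test or conclusion.

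The range of 7.3% to 9.1% for one unadjusted look (8.3% at half the data) is conditional. It rests on an assumed alpha, an assumed look time, and an option to stop or claim success that appears nowhere in the protocol. The conclusion would change if there were evidence that a by-arm efficacy look was intended or had been taken. The documents contain none.
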